7.4 Evaluation at Completion of Study Intervention

Study Visits 1 and 2 may be combined on the same day if feasible and convenient (i.e. surgery start time allows completion of Study Visit 1 tasks prior to surgery start time. If this is not possible, Study Visit 1 will occur on the day prior to surgery. Participants will fast from midnight on the evening prior to surgery.

- **7.4.1** Study Visit 1 (Day before surgery, can occur on the day of surgery if feasible for participant to arrive early)
 - 1. BESS questionnaire (Appendix D)
 - 2. Tobacco and Alcohol Use Questionnaires
 - 3. Skin symptoms per CTCAE criteria (Table 1).
 - 4. Breast skin photos, taken only in participants experiencing skin toxicity, and will focus on the area showing the skin toxicity.
 - 5. Collection of last menstrual period date for premenopausal participants
 - 6. Concomitant medications and adverse events assessment
 - 7. Compliance assessment (weighing gel dispensers) and collection of study agent
 - 8. Collection of study diary.

7.4.2 Study Visit 2 (Day of surgery, day 22-29)

On arrival the following procedures/evaluations will be performed:

- 1. Urine or serum pregnancy test (for subjects of child bearing potential) per standard of care prior to the surgery.
- 2. Medical history per treating physician
- 3. Physical exam. The source document for this may be anesthesia or surgery H&P, completed within 28 days prior to surgery.
- 4. Vital signs assessment per anesthesia assessment or pre-operative nursing evaluation
- 5. Clinical labs for renal and hepatic function including total bilirubin, AST, ALT, alkaline phosphatase, blood urea nitrogen and creatinine
- 6. Blood collection for research purposes:
 - a. Two 3 mL Blue Top tube (citrate) for coagulation panel.
 - b. Two 10mL Lavender top tubes (K₂EDTA) to obtain plasma for hormone level measurement (estradiol, progesterone, and androgens [DHEA (dehydroepiandrosterone), androstenedione, and testosterone]) and measurement of IGF-1, IGFBP-3, and SHBG. Buffy coat will be saved for DNA/RNA isolation for future pooled analyses if the subject consents to this optional study.
- 7. Blood collection should occur prior to completion of the mastectomy (i.e. if blood is not drawn prior to the patient entering the operating room, it can be drawn in the OR).
- 8. Tissue will be obtained from the DCNB as well as the surgical resection specimen for study end points.

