1.2 Secondary Objectives

- 1.2.1 To measure the breast tissue concentrations of (E) and (Z) isomers of N- desmethyl-4-hydroxytamoxifen (ENX) and 4-hydroxytamoxifen (4-OHT) at each dose (10 mg per day and 20 mg per day).
- 1.2.2 To measure the plasma concentrations of (E) and (Z) isomers ENX and 4-OHT at each dose (10 mg per day and 20 mg per day).
- 1.2.3 To measure plasma hormone levels for steroid hormones (estradiol, progesterone, dehydroepiandrostenedione [DHEA], androstenedione, testosterone) in comparison to vehicle placebo gel.
- 1.2.4 To measure serum estrogenic response to topical ENX gel therapy in comparison to vehicle placebo gel (sex hormone binding globulin and IGF pathway proteins).
- 1.2.5 To assess changes in coagulation parameters (Factor VIII, Factor IX, vWF, Protein S) in response to ENX gel therapy in comparison to vehicle placebo gel.
- 1.2.6 Using pre- and post-therapy tissue samples, to explore the potential therapeutic effects of the two doses of ENX gel in comparison to vehicle placebo gel: a) by IHC, Ki67 labelling (for cell proliferation), estrogen receptor (ER), progesterone receptor (PR) expression (for estrogen blockade); b) by expression of a panel of genes reported to change with ENX exposure (using nanostring assays).
- 1.2.7 Bank germline DNA for future pooled analyses of polymorphisms in tamoxifen metabolizing enzymes in comparison to vehicle placebo gel (optional).
- 1.2.8 To assess symptoms related to use of endoxifen gel in comparison to vehicle placebo gel, as assessed by the Breast Cancer Prevention Trial (BCPT) Eight Symptom Scale (BESS) questionnaire.

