2.3 Rationale

2.3.1 Hypotheses

Our *primary hypothesis* is that ENX gel at 20 mg daily (10 mg per breast) will be safe and tolerable as assessed objectively using CTCAE criteria, in comparison to the placebo group.

Our secondary hypotheses include 1) the breast tissue concentrations of ENX at will reach the concentrations achieved in our prior study of oral tamoxifen versus 4-OHT gel (5.8 ng/g tissue) [36]. 2) The plasma concentrations of ENX at each dose (10 mg per day and 20 mg per day) will be significantly lower than those seen in women on oral tamoxifen. 3) Plasma hormones (estradiol, progesterone, DHEA, androstenedione, testosterone) will not be changed by ENX gel use. 4) Changes in serum estrogenicity (sex hormone binding globulin and IGF pathway proteins) will be minimal, if any. 5) Changes in coagulation parameters (Factor V, Factor VIII, von Willebrand factor, Protein S) will be minimal, if any. 6) Biologic endpoints such as Ki67 labeling index, ER, and PR expression, and expression of a panel of genes reported to change with ENX exposure, will be consistent with a therapeutic effect of ENX gel. 7) Polymorphisms in tamoxifen metabolizing enzymes will not affect breast tissue ENX concentration. This hypothesis will not be tested in the current study, but germline DNA will be banked for future pooled analyses of transdermally versus orally administered tamoxifen and metabolites relative to metabolic efficiency for oral tamoxifen. Banking of germline DNA for future pooled analyses will be optional for participants. 8) Symptoms reported with the use of ENX gel will be similar between treated and placebo groups.

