5.5 Concomitant Medications

All medications (prescription and over-the-counter), vitamin and mineral supplements, and/or herbs taken by the participant will be documented on the concomitant medication CRF and will include: 1) start and stop date, dose and route of administration, and indication. Medications taken for a procedure (*e.g.*, biopsy) should not be included.

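### End-of-treatment research blood may be drawn during the operation, and the within-arm post-pre tests for hormones, SHBG/IGF and coagulation proteins cannot separate a perioperative shift from a gel effect

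*Combined protocol and SAP*

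**What the plan says.** Section 7.4.2 opens the surgery-day list with "On arrival the following procedures/evaluations will be performed". Item 7 then treats blood separately: "Blood collection should occur prior to completion of the mastectomy", and "if blood is not drawn prior to the patient entering the operating room, it can be drawn in the OR". The baseline sample comes from Screening Visit 1 (section 7.2.1).

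Objective 1.2.5 reads "To assess changes in coagulation parameters (Factor VIII, Factor IX, vWF, Protein S) in response to ENX gel therapy" and continues by naming vehicle placebo as the comparator. Objectives 1.2.3 (steroids) and 1.2.4 (SHBG and IGF proteins) name the same comparator. Section 2.3.1 expects little movement: "Changes in coagulation parameters (Factor V, Factor VIII, von Willebrand factor, Protein S) will be minimal, if any". (The two lists differ by one clotting factor, which is a separate matter.)

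Section 13.5 (3-5) gives the analysis for all three marker groups: a 95% interval for the mean post-pre difference and a test against zero. Plasma endoxifen, in 13.5 (2), is reported as an observed concentration. Section 5.5 leaves one class of drug out of the concomitant medication record: "Medications taken for a procedure". Section 10.2 sends sites to a Specimen Manual for collection details, and that manual is not among the documents.

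**The concern.** A site that follows item 7 exactly can draw one woman in pre-operative holding and another well into the operation, after anaesthesia, fluids and tissue injury. Both samples enter the analysis as the post value, against a baseline taken at a screening visit. The protocol as supplied does not ask when the draw took place relative to induction. Under 5.5, perioperative drugs would not appear in the study's medication data either.

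The coagulation objective is a question about the gel's systemic safety. If being in theatre moves these proteins, the within-arm change could show a signal that the gel did not cause, or hide one that it did. The same applies to the hormone and SHBG/IGF results, which support the claim of little systemic effect.

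**Working it through.** **The plan's own figure.** Section 13.1 gives one precision statement, for the pooled placebo group of 8: 0.5/√8 = 0.177 for a proportion, and SD/√8 for a mean. It reproduces. The plan gives no SD, effect size or power for the blood markers, so everything numerical below is illustration.

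**Inputs from the documents.** Cohorts 1 and 2 each have 8 active and 4 placebo women. Cohort 3 has 8 active and no placebo (sections 3.2.1 and 13.1). Tests are two-sided (section 13.5), and 5% is inferred from the 95% intervals.

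**Assumed inputs.** These are the share of draws made in the operating room and the size of the shift. Neither is in the documents.

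**Shift in an arm mean.** If k of 8 women are drawn in theatre and each value moves by d, the arm mean moves by (k/8) × d:
- (2/8) × 10% = 2.5%
- (4/8) × 30% = 15%
- (6/8) × 50% = 37.5%

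**Within-arm test against zero, no gel effect, every draw shifted by δ SDs of the change.** The one-sample t statistic is noncentral t with n − 1 degrees of freedom and noncentrality δ√n; for δ = 0.5 and n = 8 that is 0.5 × √8 = 1.41. Rejection rates at a nominal 5%:

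| δ | n = 8 | n = 16 |
|---|---|---|
| 0 | 5% | 5% |
| 0.25 | 9% | 16% |
| 0.5 | 23% | 47% |
| 0.75 | 45% | 80% |
| 1.0 | 68% | 96% |

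Here n = 16 stands for the 10 mg women of Cohorts 1 and 3 taken together. The plan does not say that it will pool them.

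**Only some draws shifted.** This was simulated with 4,000 trials per setting, each woman having the stated chance of a theatre draw. At a chance of one half:

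| n | Shift | t-test | Wilcoxon signed-rank |
|---|---|---|---|
| 8 | 0.5 SD | 10% | 8% |
| 8 | 1 SD | 20% | 16% |
| 16 | 0.5 SD | 16% | 14% |
| 16 | 1 SD | 39% | 36% |

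Both tests are shown because 13.5 (3-5) does not name one. At a chance of one quarter and n = 8, the t-test rates are 6% and 8%.

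**Active versus placebo on the same simulated data.** The Mann-Whitney test of 8 or 16 active women against 8 placebo women, with the same chance of a theatre draw in both arms, rejects in 4.0% to 5.5% of trials in every setting. Chance imbalance in draw timing is already included in those rates.

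**Precision of that contrast.** With noncentrality δ/√(1/n₁ + 1/n₂), a two-sample t-test has 80% power at 1.51 SD for 8 against 8, and at 1.27 SD for 16 against 8 (both doses of Cohorts 1-2 pooled).

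**The case against.** The strongest reply is randomisation. In Cohorts 1-2 allocation is blinded, so draw timing should not depend on treatment, and the objectives are already worded as comparisons with placebo. This stands as far as it goes: the contrast keeps its nominal error rate even with theatre draws. But 13.5 (3-5) does not specify the contrast, and it cannot serve Cohort 3. A reader might infer that the placebo women are of no help here. The calculation does not support that; their limit is low precision.

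Second, arrival is the default and the theatre draw is a fallback. That is correct, so item 7 should not be read as the only timing instruction. It is still an express permission.

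Third, the Specimen Manual, the PK/Biomarker Supplement cited in 9.1, or the case report forms may set a tighter time or record it. They may, and the point is conditional on that. If they do, item 7 should be brought into line with them.

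Fourth, the documents do not say how anaesthesia or surgery moves these markers. A reader might infer a rise in clotting factors that looks prothrombotic, or a dilution that flatters the low-exposure hypothesis. The documents support neither direction, and the two would pull against each other.

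Fifth, a reader might count plasma endoxifen among the post-pre changes. Section 13.5 (2) reports an observed level, so for plasma drug only the sampling conditions are in question.

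**Conclusion.** The point stands as a gap in both timing and analysis for the secondary blood endpoints 1.2.3 to 1.2.5. The plan permits samples taken under materially different conditions, does not visibly record which are which, and applies a within-arm test that cannot tell a perioperative shift from a gel effect. If half the draws carry a shift of 0.5 to 1 SD, false positives in an arm of 8 are roughly two to four times the nominal 5% with the t-test, and somewhat fewer with the signed-rank test. If no draw is made in theatre, or the shift is nil, this mechanism does no harm.

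The conclusion rests on the assumed share and size of the shift, and on the unseen manual not already settling the timing. It does not show that Cohort 1-2 samples are unusable, that any result is wrong, or that the primary skin-toxicity endpoint is affected. It matters most for Cohort 3, whose 8 women have no placebo comparator and are still to be accrued under this version.

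**What to change.** **Collection.** Amend 7.4.2 item 7 to say: *Research blood is drawn on the day of surgery before induction of anaesthesia (on arrival, in pre-operative holding, or at line placement). Record the time of the draw and the time of induction.* Align the Specimen Manual. The draw should not move to Study Visit 1. That visit may fall on the day before surgery, when the last dose is applied (Appendix C) and before the fast from midnight begins (section 7.4), so time since last dose and fasting state would vary between women. Study Visit 1 also has no scheduled blood draw, so a needle stick might be added.

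**Samples already taken in Cohorts 1-2.** Obtain induction and draw times from the anaesthesia record. Keep every sample in the main analysis, as 13.8 requires, and report a sensitivity analysis without post-induction samples. Dropping them from the main analysis would conflict with 13.8, and at k = 2 to 6 of 8 would discard 25% to 75% of an arm.

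**Analysis.** Add to 13.5 (3-5) the active-versus-placebo contrast of post-pre change with its interval for Cohorts 1-2, as the objectives already imply. Present Cohort 3 changes as uncontrolled.

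**Cost.** Two time fields, a short amendment, a little more analysis, and possibly a few missed samples in Cohort 3. No visit is added.

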7.5 Post-intervention Follow-up Period

- **7.5.1 Study Visit 3** (Post-op visit in the breast surgery clinic, day 29-50) (The intent is to have this visit 7-14 days after study visit 2):
 - 1. Vital signs assessment
 - 2. Concomitant medication follow-up assessment for those taken prior to surgery. No new concomitant medications will be recorded unless they pertain to adverse events that occurred prior to surgery.

- Adverse event follow-up assessment for those occurring prior to surgery. No new adverse events after surgery will be recorded.
- 4. Collection of last menstrual period date for premenopausal participants
- Evaluation of skin for CTCAE criteria; if ambiguity as to post-surgical change versus skin toxicity, treating surgeon and dermatologist will together assign causation to surgical or drug relationship.
- 6. Skin photos, taken only in participants who had documented skin toxicity at Study Visit 1, and will focus on the area showing the skin toxicity.

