- 3.2.2 Definition of Dose-Limiting Toxicity (DLT): for the purposes of this agent, and the anticipated need for long-term tolerability, we have used Grade 2 or greater skin toxicity as the DLT, using CTCAE criteria for the parameters shown in Table 1. The Grade 2 or greater reaction should occur at the application site for 48 hours or longer and be definitely, probably, or possibly related to the study drug to be a cause for participant withdrawal. After consultation with the NCI DCP medical monitor, a participant will be unblinded in the event of a DLT.
- 3.3 Participants will be given 1 canister of study agent, each containing 90 mL of active gel or placebo, at the baseline visit. Participants will take study agent for 21-28 days. The study will be terminated when 1) more than 2 subjects experience Grade 2 or greater toxicity (at application site for 48 hours or longer, and definitely, probably, or possibly related to study drug) in Cohort 1 and its expansion; or 2) eight subjects complete participation in Cohort 3.
- 3.4 No run-in period is planned.
- 3.5 Time points for performing study assessments for primary endpoint
- 3.5.1 Weekly phone calls to assess drug tolerability, with special emphasis on skin reactions if any. If skin reactions are reported by subjects between study visits, the participant will be asked to take a photograph (a single frontal view of both breasts, in good light). The participant will be provided a personalized link via email, where they can upload the photographs to a secure REDCap site. [name] will have access to this site and will evaluate the photos, and grade them using CTCAE criteria using the parameters outlined in Table 1. If she feels, or the participant requests, a consultation, this will be arranged to occur within the next 48 hours (or 72 hours if this happens to occur over a weekend). The NU dermatologist is [name] [name]; at MSKCC [name]; at Cedars [name]. Prior to scheduling a consultation, [name] and [name] may also be granted access to photos from participants at their institutions through REDCap.

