- 3.5.2 Baseline and end-of-intervention photos and skin toxicity assessment using CTCAE criteria. The photographs will be taken by the coordinator as a standardized single frontal view of both breasts (the view will include from the bottom of the neck to below the breasts, and from the lateral side of one breast to the lateral side of the other breast), and side views of each breast. They will be uploaded to NOTIS and viewed by [name] for scoring.

3.6 *Measurements taken to meet secondary study objectives*

Screening Visit 1: At entry for consent, review of eligibility, instructions on how to apply study agent, baseline symptom assessment, concomitant medication review, blood draw for clinical and research labs, urine or serum pregnancy test in women of child bearing potential, last menstrual period, BESS questionnaire, breast skin photos, CTCAE criteria assessment, and dispensing study agent.

Study Visit 1: Day before surgery. Symptom and adverse event assessment, concomitant medication review, last menstrual period, BESS questionnaire, breast skin photos, CTCAE criteria assessment, and study agent compliance.

Study Visit 2: Day of surgery. Blood draw for clinical and research labs, urine or serum pregnancy test in women of child bearing potential, physical exam, medical history, and tissue for research. Study visit 1 and 2 may be combined on day of surgery.

Study Visit 3: Post-operative visit. Symptom and adverse event assessment, concomitant medication review, last menstrual period, breast skin photos, and CTCAE criteria assessment.

- 3.7 Clinical procedures, lab tests and other measurements taken to monitor effects and safety of study agent.
 - Skin evaluation through history, physical examination (documented by skin photographs and CTCAE criteria). This will be performed at study entry and at the end of intervention.
 - Clinical blood tests pre and post intervention to establish good hematologic, renal, and liver function.
 - Research blood tests pre and post intervention to evaluate effects on coagulation pathway proteins and markers of systemic estrogenicity.
 - Urine pregnancy test in women with childbearing potential (pre and post intervention)
 - Breast size and body mass index (BMI) pre intervention.
 - Examination of breast tissue and plasma samples for drug concentration (at the end of intervention) and antiestrogenic effects of ENX gel (comparing samples obtained prior to and following intervention).

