7.2 Baseline Testing/Pre-study Evaluation

7.2.1 Screening Visit 1

The following will be collected:

- 1. Informed Consent
- 2. Medical History per treating physician
- 3. ECOG performance status
- 4. Prior and concomitant medication review
- 5. Vital signs assessment
- 6. Physical Exam per treating physician within 6 weeks of registration
- 7. Clinical labs for renal and hepatic function including total bilirubin, AST, ALT, alkaline phosphatase, blood urea nitrogen, and creatinine to be collected within 6 weeks prior to registration
- 8. Blood collection for research purposes:
 - a. Two 3 mL Blue Top tube (citrate) for coagulation panel.
 - b. Two 10mL Lavender top tubes (K₂EDTA) to obtain plasma for hormone level measurement (estradiol, progesterone, and androgens [DHEA (dehydroepiandrosterone),

²Required within 5 days prior to starting study treatment for females of child-bearing potential. Women of child-bearing potential whose Screening Visit 1 occurs >5 days prior to starting study agent, will have a separate office visit to conduct a second pregnancy test within 5 days of starting study agent.

³Tissue will be obtained from the diagnostic core needle biopsy (DCNB) as well as the surgical resection specimen for study end points. Though there is no physical collection of tissue at Screening Visit 1, release for acquisition of DCNB tissue will be completed at this visit.

⁴Participants who are unable to pick up the study medication will receive it via mail or courier delivery requiring signature to confirm receipt.

⁵Urine or serum pregnancy test is routinely performed for females of child-bearing potential prior to the surgery.

⁶Study Visits 1 and 2 may be combined on the same day if feasible and convenient (i.e. surgery start time allows completion of Study Visit 1 tasks prior to surgery start time). If this is not possible, Study Visit 1 will occur on the day prior to surgery.

⁷Source document will be anesthesiologist or surgeon pre-op history and physical. May have been performed on day of surgery or within 28 days prior.

⁸Participants who require a delay in surgery will be allowed to continue treatment for up to 7 additional days.

⁹ Study Visit 1 skin photos will be taken only in participant experiencing skin toxicity, and will focus on the area showing the skin toxicity.

¹⁰ Study Visit 3 skin photos will be taken only in participants who had documented skin toxicity at Study Visit 1, and will focus on the area showing the skin toxicity.

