11.1 Adverse Events

11.1.1 Reportable AEs

All AEs that occur after the informed consent is signed and baseline assessments are completed must be recorded on the AE CRF (paper and/or electronic) whether or not related to study agent.

Table 1. A modified CTCAE for assessing skin application AEs.

Table 1 Modified CTCAE for assessing skin toxicity of endoxifen gel applied to the breast skin. These	
assessments will be made on the breast skin (application site).	

	assessments will be made on t	ne breast skill (application	5,10,1
	Grade 1	Grade 2	Grade 3
Dry Skin	No erythema or pruritus	With erythema or pruritus	With erythema and pruritus
Pain of Skin	Mild pain	Moderate pain	Severe pain
Photosensitivity	Painless erythema	Mild to moderate pain with erythema	Erythema with blistering
Pruritus	Mild, requiring topical intervention	Intense, with changes from scratching, oral intervention needed	Intense, constant, limiting ADL or sleep, oral steroids needed.
Rash maculopapular	Macules or papules <25% of treated area, with or without symptoms (pruritus, burning, tightness)	Macules or papules >25% of treated area, with or without symptoms (pruritus, burning, tightness), limiting instrumental ADL	Macules or papules > 25% of treated area, with or without symptoms (pruritus, burning, tightness), limiting self-care ADL
Urticaria	Asymptomatic or mild symptoms, not requiring therapy	Moderate; limited local therapy needed, limiting instrumental ADL	Urticarial lesions covering >30% of application area; oral or IV intervention needed

11.1.2 AE Data Elements:

The following data elements are required for AE reporting.

- AE verbatim term (AEs which occur on the breast should include "application site" in the verbatim term).
- NCI Common Terminology Criteria for Adverse Events version 4.0 (CTCAE v4.0) AE term (MedDRA lowest level term)
- CTCAE (MedDRA) System Organ Class (SOC)
- · Event onset date and event ended date
- Treatment assignment code (TAC) at time of AE onset
- Severity grade
- Attribution to study agent (relatedness)
- Whether or not the event was reported as a SAE
- Whether or not the subject dropped due to the event
- Outcome of the event

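### Section 7.5.1 ends the recording of new adverse events at surgery while 11.1.1 sets no end date, so a new drug-attributed skin reaction found at Study Visit 3 may have no AE entry

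*Combined protocol and SAP*

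**What the plan says.** Section 7.5.1 lists the work of Study Visit 3. Item 3 limits AE work to follow-up of events that began before surgery, then adds: "No new adverse events after surgery will be recorded". Item 2 sets a parallel limit: "No new concomitant medications will be recorded unless they pertain to adverse events that occurred prior to surgery". Item 5 nevertheless orders a skin assessment: "Evaluation of skin for CTCAE criteria; if ambiguity as to post-surgical change versus skin toxicity, treating surgeon and dermatologist will together assign causation", the choice being surgery or drug. Item 6 restricts photographs: "Skin photos, taken only in participants who had documented skin toxicity at Study Visit 1". Footnote 10 of the Schedule of Events repeats this: "Study Visit 3 skin photos will be taken only in participants who had documented skin toxicity at Study Visit 1".

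Section 11.1.1 gives the general rule, related or not: "All AEs that occur after the informed consent is signed and baseline assessments are completed must be recorded on the AE CRF". Section 11 states no end to this period for non-serious events.

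Section 3.6 lists AE assessment, concomitant medication review, breast skin photos and CTCAE assessment at Study Visit 3 without any of these limits.

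For the primary endpoint, 3.5 is headed "Time points for performing study assessments for primary endpoint". It names the weekly calls (3.5.1) and "Baseline and end-of-intervention photos and skin toxicity assessment using CTCAE criteria" (3.5.2). Section 3.7 places the skin evaluation at study entry and end of intervention. Section 13.4 names neither a data source nor a time window.

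**The concern.** Dermal tolerability and safety of the gel is the primary objective (1.1) and primary endpoint (8.1). The plan sends a clinician to examine the skin one to two weeks after surgery and foresees that some findings will be put down to the drug. It then has a rule under which a finding of that kind, if new and non-serious, is not entered as an adverse event. Two sites could handle the same reaction differently, one following 7.5.1 and the other 11.1.1, and each could point to the protocol in support.

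Surgery does not remove the question. Gel goes on both breasts (4.2.10) and mastectomy may be unilateral (3.1), so a treated, unoperated breast can remain. Section 8.2 also foresees nipple-sparing procedures in which skin is not resected.

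At stake is the completeness and consistency of the AE record for late skin reactions in what Section 2.2 calls a first-in-human study of this gel in the US.

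**Working it through.** The plan gives no figure to reproduce here. The check compares the passages and works out the length of the gap.

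**1. Can both recording rules be followed?** Take a new, non-serious AE that starts after surgery and before Study Visit 3.
- 11.1.1: it must be recorded, because it follows consent and baseline.
- 7.5.1 item 3: it must not be recorded, because it is new after surgery.

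Both cannot be followed unless 7.5.1 is read as the end date that 11.1.1 lacks. No cross-reference says so.

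**2. What happens if 7.5.1 prevails?** Take a new skin reaction with onset after surgery, attributed to the drug.
- Skin grade: assessed. Item 5 requires it, and the Schedule of Events lists CTCAE skin toxicity at Study Visit 3 in a row separate from adverse events.
- AE entry: barred by item 3.
- Visit 3 photo: excluded by item 6 and footnote 10 unless toxicity was documented at Study Visit 1; listed without restriction in 3.6.
- Medication given for it: barred by item 2, although Table 1 grades pruritus and urticaria partly by the treatment needed.

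**3. What is not affected?**
- Serious events: 11.2 has its own reporting route with no cut-off at surgery.
- Reactions that began before surgery: item 3 keeps them under follow-up, even if first noticed at Study Visit 3.

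**4. How long is the gap?**
- Surgery on day 22–29 (7.4.2), Study Visit 3 intended 7–14 days later (7.5.1).
- Earliest: 22 + 7 = day 29. Latest without delay: 29 + 14 = day 43. With the permitted 7-day delay: 43 + 7 = day 50. This agrees with the stated day 29–50.
- The last gel application is the day before surgery (5.2.2), so Study Visit 3 falls 7 + 1 = 8 to 14 + 1 = 15 days after last exposure.

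**5. Whom can a change still reach?** Section 13.1 describes Cohorts 1 and 2 as complete (12 + 12 = 24 women), with 8 to be accrued in Cohort 3, for a total of 32. The combined placebo group (4 + 4 = 8) and all women on 20 mg are in the completed cohorts. Data collected under a new rule in Cohort 3 alone would therefore have no placebo or 20 mg counterpart.

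**The case against.** The strongest reply is that nothing conflicts: 11.1.1 says when recording starts and 7.5.1 says when new recording stops. Items 2, 3 and 6, footnote 10 and the day-60 contact, which collects only the menstrual date, fit a deliberate cut-off at surgery. This is a fair reading and may be what was intended. It does not settle the matter. 11.1.1 would still lack the matching end date, 3.6 would still differ, and item 5 would still produce drug attributions that cannot be entered as AEs.

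The exposed case is also narrow: non-serious, new after surgery, after the last dose, and attributed to the drug. No remaining dose decision depends on it, since the Cohort 3 dose is set and the toxicity termination rule in 3.3 concerns Cohort 1 and its expansion. All of this stands and limits the weight of the point.

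A reader might infer that a missed reaction would move the primary incidence, since one woman in a group of 8 is 1/8 = 12.5 percentage points. The documents do not support that inference. Sections 3.5 and 3.7 place the primary-endpoint skin assessments at the weekly calls, baseline and end of intervention, so a reaction starting after surgery lies outside those time points. Section 13.4 does not repeat this, but its silence is no ground for assuming that Study Visit 3 counts.

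A reader might also infer that such a reaction would go wholly unseen or could never be photographed. That too is unsupported. The grade is assessed at Study Visit 3. Section 3.6 lists photos at that visit without restriction, and 3.5.1 asks for a participant photo when a reaction is reported between visits, though it is written for the weekly calls.

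**Conclusion.** The point holds, within limits. 7.5.1 and 11.1.1 give different rules for a new AE after surgery and must be reconciled with each other and with 3.6. If 7.5.1 prevails, a new, non-serious, drug-attributed skin reaction starting after surgery would be graded but would have no AE entry. It would have no Visit 3 photo under item 6 and footnote 10 unless toxicity was documented at Study Visit 1.

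The size is a recording gap from surgery to Study Visit 3, ending about 8 to 15 days after last exposure. The documents give no rate for such reactions, so no expected number is claimed, and no change in the 13.4 estimate is claimed. The conclusion assumes that sites apply the detailed visit rule over the general one; sites that follow 11.1.1 would have no gap but would differ from the others. A correction is warranted because a stated rule can keep safety information on the trial's main question out of the AE record, at a visit that takes place anyway.

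**What to change.** - State one AE recording period, with the same end date, in 7.5.1 and 11.1.1, and align 3.6, items 2, 3 and 6 of 7.5.1, and footnote 10 to it.
- Through Study Visit 3, record new skin findings on a treated breast as AEs, using the surgeon and dermatologist attribution already in item 5. Photograph them and capture any medication given for them. Leave the SAE route in 11.2 as it is.
- State in 13.4 that the incidence estimate uses the 3.5 time points. List drug-attributed findings with post-surgery onset separately, identified by AE onset date.
- Document which recording rule Cohorts 1 and 2 followed. Do not compare post-surgery findings across doses or with placebo unless they were recorded in the same way.

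The cost is wording changes plus a few entries and photos for the 8 Cohort 3 women at an existing visit. Onset date and relatedness are already required data elements (11.1.2); the CRFs themselves are not in the documents. The downside is that some entries will be attributed to surgery, and the new data may be descriptive for Cohort 3 only.
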